#### Participating teams of practitioners

LAs were asked to identify teams they would like to have participate in the efficacy trial as teams that meet the following two conditions:

- a) frequently support young people aged 11-18 at medium to high risk of contextual harm
- b) consent to train in and deliver Your Choice should they be randomly assigned to deliver the experimental condition.

Across the whole study, there are 130 teams involved in one of the three batches of the randomisation. As Table 2 details, these 130 teams include 7 teams that only participated in the pilot trial, 93 teams that will only participate in the efficacy trial, and 30 teams that will participate in both. In the latter group, the 16 teams that acted as controls in the pilot were pulled back into the randomisation pool for the efficacy trial. 8 of these teams were randomised to retain their control status. But 8 others were randomised to switch to treated status. From the point of the view of the randomisation (and power calculations), these teams amount to new teams in efficacy so while the number of unique teams is 130, the effective number of teams is 138 (since these 8 teams count as 8 controls during the pilot and as 8 treated teams during efficacy).

Table 2: Teams involved in the whole evaluation (including internal pilot)

Type of teams based	Number of unique teams		Number of	effective	Number	of	
on involvement in pilot	and breakdown		teams	and	LAs		
and efficacy phases	between treated	control	and	breakdown control and		represent	ed

A. Teams that only recruited during the pilot trial	

7 unique teams, including:

• 3 control

• 4 treated

	

15 effective teams including:

11 control

4 treated

	5 LAs
B. Teams that are only expected to recruit during the efficacy trial	

93 unique teams, including:

47 control

46 treated

	

101 effective teams including:

47 control

54 treated

	25 LAs
C. Teams that both recruited during the pilot trial and are expected to recruit during the pilot trial	
 
30 unique teams, including:
 
8 control in pilot, control in efficacy
 
8 control in pilot, treated in efficacy
 
14 treated in pilot, treated in efficacy
 
	
 
24 unique teams, including:
 
8 control in pilot, control in efficacy
 
14 treated in pilot, treated in efficacy
 
	18 LAs
Total across pilot and efficacy	130 unique teams	138 effective teams	29 LAs

#### Teams of practitioners involved in efficacy phase

We provide further details on the 123 teams (type B and type C above) involved in the efficacy phase of the trial and on the randomisation performed to allocate treatment to those teams whose condition could be randomised in this round. Table 3 below breaks down these 123 teams into six types, depending on their status in previous phases of delivery. It shows that 22 teams (of types 5 and 6) cannot be randomised in efficacy because they were randomised into treatment during previous batches of randomisation and so can only continue acting as a treated team in efficacy. Among the other 101 teams (of types 1, 2, 3, 4), randomisation cannot take place in LAs where there is only 1 team of this type. This happens in 6 LAs (Barnet,

Bexley, Havering, Hounslow, Lewisham, Newham). This means that we end up with 95 teams for randomisation in the efficacy stage of the study.

Table 3: Teams involved in the efficacy stage of the evaluation

Type of team	Number of teams
1. New teams (these teams were never included in the HO or pilot batches of randomisation, nor did they recruit any participant in previous phases)	69
2. Teams that were randomised into control during the Home Office phase	3
3. Teams that were randomised into control during the plot phase	28
4. Team that was non-randomly selected as control during the pilot phase	1
5. Teams that were randomised into treatment during the Home Office phase	4
6. Teams that were randomised into treatment during the pilot phase	18
Total	123

As for the pilot phase, the 28 LAs that are participating in the efficacy phase will be required to sign a Grant Agreement with the Violence Reduction Unit outlining the funding they will receive, as well as minimum requirements attached to their participation, including their willingness for their teams to partake in the randomisation, their readiness to share data about participants' background information and compliance with the study, their willingness to facilitate survey data collection, and the readiness to deliver Your Choice during the duration of the pilot.

#### Participating young people

Participants will be recruited among the young people allocated to be supported by participating teams who meet the following eligibility criteria:

- a) age 11-18 years old (inclusive) at the time of recruitment;
- b) at medium to high risk of contextual harm and referred to LA services with a view of mitigating such risk. This assessment will need to be quality assured by a MACE/pre-MACE panel or by the practitioner's team manager.

Recruitment of young people to the study will be done by the young person's lead practitioner. The practitioner provides information about the study using the information sheet and recruitment video. After discussing what participation would entail in one or several sessions, the practitioner will ask the young person to sign a consent form. For young people aged 11-15 years old, the practitioner will also involve the young person's parent in the recruitment discussion and require the young person's parent or guardian to sign a parental consent form.

#### Rationale for planned number of participants

The planned number of participants in the efficacy phase is 1,857. This number includes:

- 179 young people recruited in randomised teams during the pilot phase (among them, 83 young people have endline young people questionnaires completed at the time of writing).
- 1,678 young people expected to be recruited in randomised teams during the efficacy phase (Aug 2023 – December 2024).

We believe the expected number of participants during the efficacy phase is realistic for the following reasons. First, these numbers have been discussed by the evaluation team in one-to-one conversations or email with each LA. Second, several LAs have purposely provided lower bounds to the numbers they think they can actually recruit in order to be realistic and successful in meeting these numbers. Third, the efficacy trial is planned to involve about five times as many randomised teams as the pilot trial did, and to last roughly 3 to 4 times as long as the pilot trial. We therefore think that it is reasonable for the number of participants in the efficacy trial to be at least 10 times higher than the pilot trial, or around at least 1,600 young people.

#### Settings of intervention delivery

-

<sup>5 At the time of writing, 4 Local Authorities had not confirmed their expected numbers of participants and we therefore made conservative assumptions about their expected numbers of participants.

Sessions between young people and practitioners can take place in a variety of settings, from the young person's home, to a council building (e.g. a youth or community centre, school) to a public place (e.g. park).

#### Settings of data collection

Baseline and endline young people questionnaires will be collected during sessions between the young person and their lead practitioner (and potentially their parent or guardian). As mentioned above, these sessions can take place in a variety of settings. Young people will complete the online forms and questionnaires on the practitioners' work device which can be a phone, tablet or computer. Practitioners will fill out the baseline and endline practitioner questionnaires as well as session forms on their work devices.

#### Sample size calculations

Based on LAs' plans for the efficacy trial, the expected analytical sample will have two features that are important to consider for inference:

- There will be a small number of units of randomisation (teams) within strata (LA): Among the 29 LAs participating in the whole evaluation (internal pilot + efficacy), the median number of teams per LA is 3 (the average 4.6), with all but 2 LAs having 10 or fewer teams involved in the trial (Brent has 12 teams and Barking and Dagenham has 21 teams).
- Units of randomisation (teams) have more than 10 observations on average: Based on the conservative predictions of participating young people provided by Local Authorities so far, the average expected number of participants per team is 13.7

De Chaisemartin and Ramirez-Cueller (2022) show that in stratified cluster RCT where the number of units of randomisation (teams) is small (10 or fewer) within strata (Local Authorities), the regular practice of clustering standard errors at the unit of randomisation can lead to downward bias in estimates of the variance of the treatment effect, resulting in over-rejecting the null hypothesis (of no effect). They advise that standard errors should be

<sup>6 Even after removing the 6 teams that recruited in the pilot but did not collect any endline data, the median number of teams per LA is also 3 (the average if 4.5).

<sup>7 After considering the actual attrition at endline in the pilot (54%) and the expected 30% attrition rate at endline in the efficacy, we would have 9.4 observations per team on average.

<sup>8 De Chaisermartin, C. and Ramirez-Cueller, J. (2022). "At what level should one cluster standard errors and small-strata experiments?", National Bureau of Economic Research WP 27609, http://www.nber.org/papers/w27609

clustered at the strata level (LA) when RCTs have this type of configuration (and this result holds whether or not strata fixed effects are controlled for).

We are not aware of any software allowing us to perform power calculations that take these issues into account. In order to account for the exact nature of our dataset and for these technical complexities, we therefore opted for calculating the Minimum Detectable Effect associated with 0.8 power via simulations programmed in STATA and adapting the procedure suggested in McConnell and Vera-Hernandez (2015). The simulation code used to perform these calculations is enclosed but we describe the steps used to perform these simulations below.

Each simulation is characterised by five parameters:

- Standard deviation of the outcome (σ)
- Intra-cluster correlation (ρ)
- Minimum Detectable Effect (β)
- Attrition rate (r)
- A threshold on the continuous outcome above which the binary indicator takes the value 1 and 0 otherwise  $(\eta)$

Each simulation is based the following steps:

- 1. Randomise teams to be newly randomised to treated or control within each LA with 50-50 split.
- 2. In LAs that have an odd number of teams to randomise, we randomly select whether (n+1)/2 or (n-1)/2 teams would get treated (where n is the number of teams to randomise)
- **3.** Generate a normally distributed random variable at the Local Authority level,  $\theta_j$ , of mean 0 and variance  $\rho\sigma^2$
- 4. Generate a normally distributed random variable at the young person level,  $\epsilon_{ij}$ , of mean 0 and variance  $(1-\rho)\sigma^2$
- 5. Implement the following data generation process for the outcome Y:

$$Y_{ij} = \beta T_{ij} + \theta_j + \epsilon_{ij}$$

where  $T_{ij}$  =1 if participant i is recruited in a treated team and 0 in a control team

<sup>9 In cases where clusters are small (fewer than 10 observations per unit of randomisation on average), estimates of the standard errors should not adjust for degrees of freedom. This is not the case we expect even under the conservative projections in terms of participating young people.

<sup>10 McConnell, B and Vera-Hernandez, M. (2015). Going beyond simple sample size calculations: a practitioner's guide. London: Institute for Fiscal Studies. Available at: https://ifs.org.uk/publications/going-beyond-simple-sample-size-calculations-practitioners-guide

- 6. Create a binary outcome  $D_{ij}$  such that it takes the value 1 if the score above is above a particular threshold  $\eta^{11}$  and 0 otherwise
- 7. Estimate OLS regressions of the chosen outcome (continuous  $Y_{ij}$  or binary  $D_{ij}$ ) on the treatment dummy, clustering the standard errors at the LA level, with or without controlling for Local Authority fixed effects, on a randomly selected sample of observations of size (1-r) of the expected number of study participants in order to simulate a random attrition rate r to which we add the 83 observations from pilot that have endline data.
- 8. Repeat steps 1 through 6 1000 times and compute the power as the proportion of times the coefficient  $\beta$  is significant at the 95% level.

As part of this exercise, we wanted to explore the power implications of controlling for a lagged (baseline) outcome. Instead of making additional assumptions to simulate such baseline outcome, we instead performed the simulation above with smaller values of the variance of the outcome variable and of the ICC in order to mimic the effect of controlling for a lagged outcome on these parameters as estimated using data from the pilot period.

Table 4: Values picked for parameters in simulations and justification (in italics)

	Simulation 1	Simulation 2	Simulation 3	Simulation 4
	Not controlling for lagged outcome	Controlling for lagged outcome	Not controlling for lagged outcome	Controlling for lagged outcome
Attrition rate (r)	30%		40%	
	(pilot attrition rate is of 50%)			
Standard deviation of	1 (standardised	0.5 (estimated on	1 (standardised	0.5 (estimated on
	outcome so that $\theta$ is	relevant endline SDQ	outcome so that β	relevant endline

<sup>11 This threshold is chosen such that the mean of D is equal to the probability of observing our primary outcome in the baseline pilot data.

 This step is to report power calculations for the binary outcome based on the continuous score, though the data generating process assumed here only enables us to simulate average impacts on the continuous score and hence may miss possibly stronger impacts the intervention may have at the top of the distribution

the outcome (σ)	to be interpreted in units of SD)	score after controlling for relevant baseline SDQ and treatment variable)	is to be interpreted in units of SD)	SDQ score after controlling for relevant baseline SDQ and treatment variable)

#### *Primary population of interest*

The primary population of interest will be young people age 11-18 referred to their Local Authorities for support and at medium to high risk of contextual harm. The Local Authorities' plans in terms of teams and expected numbers of participants in each team were used to simulate data on participants.

Table 5 provides information about key aspects of this data-set. The number of teams included in the power calculations is 132 (as opposed to 138) because 6 teams that recruited in the internal pilot do not have any endline questionnaire data on their participants. Since the primary outcome is from the endline questionnaire, we remove these 6 teams from the

data. We assume that all teams involved in the efficacy trial will recruit participants and collect some endline data.

The number of participants in the power calculations is 1761 (as opposed to 1,857 because it removes the 96 pilot participants that do not have endline data).

Table 5: Structure of the data used to perform power calculations

		PARAMETER
Average cluster size (if clustered)		Average number of participants per cluster (team): 13
	Intervention	70
Number of clusters (teams)	Control	62
	Total	132
	Intervention	960
Number of participants	Control	801
	Total	1761

Note that although randomisation during the efficacy phase will allocate teams to training and control on a 50-50 basis, legacy randomisation from the Home Office and pilot phases mean more teams are trained than control. It should be highlighted, however, that this imbalance across teams is expected to contribute to a more even distribution of young people across randomisation arms given that Your Choice demands more time being dedicated to each young person, so treated teams do not have the capacity to accept as many young people as control teams over a limited period.

The results of these simulations allow us to pin down the MDE under the below assumptions about power, significance level and the type of test we want to perform and under different assumptions about the attrition rate and about whether Local Authority fixed effects are controlled for in the regression.

Table 6: Minimum Detectable Effect on primary outcome (binary indicator for high to very high range of conduct problems) under the assumption we do not control for lagged outcome

Alpha 	0.05		
Power	0.8		
One-sided or two-sided?	Two-sided		
ICC	0.12		
Variance of continuous score	1		
	Attrition rate = 30%	No strata fixed effects	MDE = 0.17
Continuous score of externalising difficulties (standardised to have SD 1)		Strata fixed effects	MDE =0.16
	Attrition rate = 40%	No strata fixed effects	MDE =0.18
		Strata fixed effects	MDE =0.17
Binary score for scoring in high or very high range on conduct problems (probability of outcome in control group assumed to be 25%)	Attrition rate = 30%	No strata fixed effects	MDE = 24% of control mean
		Strata fixed effects	MDE = 23% of control mean
	Attrition rate = 40%	No strata fixed effects	MDE = 25% of control mean
		Strata fixed effects	MDE = 25% of control mean

-

<sup>13 Please adjust as necessary for trials with multiple primary outcomes, 3-arm trials, etc., when a Bonferroni correction is used to account for family-wise errors.

Table 7: Minimum Detectable Effect under the assumption we do control for lagged outcome that reduces the variance of the underlying outcome to 0.6 and the ICC to 0.05

21 1 14	0.05		
Alpha 	0.05		
Power	0.8		
One-sided or two-sided?	Two-sided		
ICC	0.05		
Variance of continuous score	0.6		
	Attrition rate = 30%	No strata fixed effects	MDE = 0.12
Continuous score of externalising difficulties		Strata fixed effects	MDE = 0.12
(standardised to have SD 1)	Attrition rate = 40%	No strata fixed effects	MDE = 0.13
		Strata fixed effects	MDE = 0.13
Binary score for scoring in high or very high range of the conduct problem scale	Attrition rate = 30%	No strata fixed effects	MDE = 24% of control mean
		Strata fixed effects	MDE = 24% of control mean
	Attrition rate = 40%	No strata fixed effects	MDE = 25 % of control mean
		Strata fixed effects	MDE = 25% of control mean

-

<sup>14 Please adjust as necessary for trials with multiple primary outcomes, 3-arm trials, etc., when a Bonferroni correction is used to account for family-wise errors.

### Discussion of MDEs in the context of the pilot trial and of the literature

The power calculations in Table 6 above indicate that, under a 30% attrition rate, we could detect with 80% power a minimum effect of 24% of baseline probability to be in the high to very high range of conduct problems.

This MDE is within the range of impacts suggested by the endline data well below the effects of CBT interventions on externalising behaviours, such as Attention Deficit Hyperactivity Disorder, Conduct Disorder and Oppositional Defiant Disorder, which are reported in the literature and which range around 60-70% (Gaffney, Farrington and White, 2021.

Using the pilot data on all teams (both randomised and non-randomised in order to maximise the sample size), we estimate that the impact of the intervention is a 34% reduction in the likelihood of a young person to be in the high to very high range of the conduct problem scale of the SDQ. (This coefficient is robust to the inclusion of the baseline outcome as control). Although this impact is not statistically significant, it is of higher magnitude than the MDE the whole study is powered to detect.

Overall, based both on the suggestive evidence from the pilot as well as from the literature on CBT interventions, we think the minimum effect the trial would be powered to detect is within the range of reasonable effects to expect from the Your Choice intervention.

#### **Outcome measures**

The baseline and outcome measures that will be used in this trial are described in Table 1. Baseline measures will be gathered shortly after recruitment in week 1, using instruments in the baseline surveys of young people and practitioners. Outcome measures will be assessed at endline, in week 20 after recruitment, using the similar instruments in the endline surveys of young people and practitioners.

#### **Baseline measures**

As described in Table 1 and below in relation to the outcomes, these include measures of internalising problems (emotional problems and peer problems), externalising problems (conduct problems and hyperactivity), prosocial behaviour, prosocial identify, social connectedness, self-reported and practitioner-reported perceptions of young person's safety. All are measured as part of the baseline survey of participants and practitioners, taken shortly after recruitment at week 1. The instruments are exactly the same as those used at in the endline surveys for primary and secondary outcomes, explained below.

#### **Primary outcome**

Our primary outcome is a measure of conduct problems based on scores from the Strengths and Difficulties Questionnaire (Goodman et al., 1997). To provide a rich picture of potential non-linearities in the impact and insights on whether young people in the high to very high zone of the scale benefit the most, we will measure conduct disorder by an indicator for the high or very high range on SDQ conduct problems subscale, where we will be using the fourfold categorisation provided by the SDQ developers in identifying high and very high ranges for these subscales. This outcome will be measured for all participants as part of the young person endline survey, taken at week 20 after recruitment.

The association between the SDQ conduct problems subscale and disruptive behaviour including violent and non-violent deliquency has been demonstrated in the existing literature (e.g Spaan et al 2023, and references therein). As explained earlier in this document (see discussion under Research Question 1), we opted for a categorical variable rather than the continuous index to better capture effects on the margin that is arguably the most relevant in assessing the success of Your Choice given the high pre-disposition for violent behaviour and rule breaking of individuals scoring in the abnormal range for this subscale. We expect the impacts of a violence reduction programme to vary by conduct difficulties given their association with violent behaviour. The alternative of considering the continuous conduct problems index for primary outcome would therefore run into the risk of diluting estimated effects of the impact of the programme and fail to reveal the impact for the sub-group that may benefit the most given the nature of the intervention.

Relative to actual measures of criminal and violent activity, the SDQ conduct problem scale has at least three advantages. First, information on this outcome is readily available at the end of the participation period while criminal activity takes time to (gradually) build up. Hence it is favoured in cases when there is urgency in learning about the impact of the intervention. Second, impacts may also be more visible on this measure than on criminal activity even in the medium run, given the low frequency of crime and the fact that conduct problems are likely at the forefront of the causal chain of effects of the intervention. In a setting where the size of the experiment may compromise what can be identified, it is crucial to identify a primary outcome that promises that impacts can be detected. And third, it is a more adequate measure to capture effects both on violent behaviour and on vulnerability to be a victim of violence. Vulnerable youth is also a target group of Your Choice and one for which crime data may not provide insights on the impact of the programme.

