# 1. Can an intervention informed by CBT techniques and practices, and delivered by trained frontline practitioners, reduce conduct problems among young people most at risk of being affected by violence?

This is the main research question, focusing on the impact of Your Choice on the primary outcome – an indicator for scoring in the high and very high range in the conduct problems subscale from the Strengths and Difficulties Questionnaires (SDQ).

The SDQ conduct problems subscale is a measure of children's ability to behave in a socially acceptable manner, considerate of others. Scores in the abnormal range of this subscale are highly prevalent among the target population, as shown in the Your Choice Internal Pilot Report. They have also been related to aggressive behaviour and predisposition to rule breaking (Essau et al. 2012, Yao et al. 2008), and are likely an important predictor and precursor of disruptive and criminal behaviour (Spaan et al. 2023).

This combination of factors explains our choice of primary outcome. Specifically, we expect that successful violence reduction interventions are especially effective among individuals scoring in the abnormal range of the SDQ conduct problems subscale, and that conduct problems are at the forefront of the causal chain of effects that may ultimately see violence reduction result from the intervention. Focusing on the most relevant part of the scale seems most adequate for the purpose of detecting changes in predisposition to aggressive and violent behaviour. The alternative of considering the continuous conduct difficulties index runs into the risk of diluting effects by averaging over heterogeneous groups by conduct difficulties. Other scales in the SDQ, such as that measuring prosocial behaviour, though certainly relevant to provide a comprehensive characterisation of the effects Your Choice and to explore its potential mechanisms, are not as directly and closely related to the ultimate goal of violence reduction, and hence will be considered secondary outcomes.

Our primary outcome will be measured at endline in the participant's survey administered at week 20 after recruitment.

The null hypothesis we will be that there is no difference in this outcome between young people allocated to Your Choice and young people allocated to business as usual.

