    - Have a more prosocial behaviour? The outcome of interest will be the SDQ prosocial behaviour scale, measured as part of the endline young person questionnaire in week 20 after recruitment.
  - Have a stronger prosocial identity? The outcome of interest will be the ProSocial Identity Scale, measured as part of the endline young person questionnaire

4. Do the impacts of being allocated to a team trained in Your Choice differ by gender, age, ethnicity, special education needs, level of risk assessed by the practitioner?

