Step 6. Investigation of potential mechanisms through which Your Choice affects externalising behaviour, arrests or risk assessment. We will regress each of the other secondary outcomes measured at endline (week 20 after recruitment) on a treatment indicator, the baseline value of that variable where available, other observed characteristics where imbalances at baseline were found (steps 1 and 2), and local Authority fixed effects. This will provide suggestive evidence on potential mechanisms underlying identified responses in externalising difficulties and criminal behaviour and risk, as detailed in the Logic Model. Effects will be shown in standard deviation units. Standard errors will be clustered at the local authority level and we will show the 95% confidence interval for the estimated effect. This analysis addresses research question 3. We will not run a fully fleshed mediation analysis because we do not have exogenous variation to independently vary the mediators.

Step 8. Heterogeneity analysis of the impact of Your Choice on the primary outcome (conduct problems) and criminal activity (possibility of arrest). This will be carried out by adding interaction terms between the treatment indicator and variables describing key demographic and contextual factors. Specifically, we will interact the treatment indicator with age, gender, ethnicity, special education needs and practitioner risk assessments at baseline. This analysis will address research question 4.

15

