#### Subgroup analyses

We will explore heterogeneous treatment effects by age, race/ethnicity, gender and practitioner risk assessment (when sample sizes allow this to be meaningfully done). Specifically, we will run separate models and test for statistically significant differences in effects across the following subgroups:

- Age 11-15 vs Age 16-18.
- White vs Non-White specifically, we would expect to compare those of Black backgrounds to those of White backgrounds and compare those of South Asian backgrounds to those of White backgrounds. This is on the basis that those from minoritised backgrounds may face more structural challenges that may impede the impact of Your Choice.
- Males vs Females.
- Medium vs High Risk based on baseline practitioner risk assessment (as per the baseline practitioner survey).

Note that the trial will not be powered to detect differences in impacts between any of these subgroups, so this analysis will be considered exploratory rather than definitive.

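### The week-20 high/very-high indicator cannot show whether young people with high baseline conduct scores benefit most, and no planned analysis splits the effect by baseline conduct status

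*Protocol*

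**What the plan says.** Under Primary outcome, the protocol says "we will measure conduct disorder by an indicator for the high or very high range on SDQ conduct problems subscale", and one stated purpose is "insights on whether young people in the high to very high zone of the scale benefit the most". It adds that the continuous index could "fail to reveal the impact for the sub-group that may benefit the most given the nature of the intervention". Research question 1 argues the same way: successful programmes are expected to be "especially effective among individuals scoring in the abnormal range of the SDQ conduct problems subscale". On timing and coverage, the Primary outcome section states: "This outcome will be measured for all participants as part of the young person endline survey, taken at week 20 after recruitment".

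The estimand is one overall intention-to-treat coefficient (Protocol, Analysis Step 3; SAP, Primary outcome analysis). The baseline value of the same indicator is planned for week 1, before Your Choice starts, and enters the model additively as Y_i0. There is no product of treatment and Y_i0.

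The moderators are listed in three places:

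- Research question 4 asks whether impacts "differ by gender, age, ethnicity, special education needs, level of risk assessed by the practitioner".
- Protocol Step 8 says "we will interact the treatment indicator with age, gender, ethnicity, special education needs and practitioner risk assessments at baseline".
- SAP, Subgroup analyses, says "We will explore heterogeneous treatment effects by age, race/ethnicity, gender and practitioner risk assessment" and calls this work exploratory and not powered.

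Baseline conduct status is in none of them. The SAP's robustness checks change covariates and the link function only.

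**The concern.** The protocol names conduct severity as the characteristic by which it expects the effect to vary, and presents the outcome definition as the way to see that. An outcome category observed after treatment does not record who started in that category. Eligibility rests on age and risk of contextual harm, with no conduct threshold, so the sample mixes young people above and below the cut-off at baseline.

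A null overall result could therefore mean no effect, or an effect in the baseline-high group that is averaged with none in the rest. A positive result could reflect recovery, prevention of new high scores, or both. If the split by baseline conduct is added only after results are seen, it will be post hoc on the protocol's own leading expectation.

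**Working it through.** **Inputs.**

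- Scenario 1: outcome mean 0.30 and MDE 24% (SAP Tables 4 and 6). Protocol Table 4 also uses 0.3, although Protocol Table 6 prints 25%. There are 1,678 expected efficacy recruits, 30% attrition and 83 pilot observations, with arms in the ratio 960:801 (Protocol, Sample size calculations).
- Scenario 2: mean 0.60 and MDE 22% (SAP Tables 4 and 6). The analysed sample is 1,094, with arms in the ratio 937:626.
- Test: two-sided 5%, 80% power, so the multiplier is 1.96 + 0.84 = 2.80.
- Baseline-high share p: 0.6 comes from baseline data. Reading 0.3 as a baseline share is an assumption, because it comes from baseline and endline pilot data combined. The SAP uses both values as control-group means.
- Control endline rates by baseline group are not in the documents and are assumed below.

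**1. The plan's own figure.** N = 0.7 × 1,678 + 83 = 1,258. A two-proportion calculation at 0.30 without a design effect gives an MDE of 7.0 points (23.3%), and power of 0.82 at 24%. A simulation following the plan's steps (area-level random effect with ICC 0.12, area fixed effects, area-clustered errors, assumed layout of teams) gives power 0.78 at a 23.7% reduction. The stated 24%, or 0.24 × 0.30 = 7.2 points, is reproduced.

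**2. What the overall coefficient identifies.** Overall effect = p × d_high + (1 − p) × d_low. That is one equation in two unknowns. With p = 0.3 and assumed control endline rates of 0.70 (baseline-high) and 0.13 (others), so that 0.3 × 0.70 + 0.7 × 0.13 ≈ 0.30:

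| Pattern | d_high | d_low | Overall |
|---|---|---|---|
| Recovery only | 0.072/0.3 = 0.24 | 0 | 0.072 |
| Equal effect | 0.072 | 0.072 | 0.072 |
| Prevented entry only | 0 | 0.072/0.7 = 0.103 | 0.072 |

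All three are feasible and give opposite answers to who benefits most. The additive Y_i0 term does not separate them.

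At p = 0.6, recovery only implies 0.132/0.6 = 22 points. Here 13.2 points is 22% of 0.60. The SAP text prints 10.8 points for the same scenario, which would imply 0.108/0.6 = 18 points; the two figures must be reconciled. Prevented entry only needs 0.132/0.4 = 33 points. That is impossible if the others' control rate is 0.30, and possible at 0.45.

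**3. Power for the contrast, relative to the overall test.** Let V be the variance of the overall estimate. With equal residual variance and design effect, the stratum variances are V/p and V/(1 − p), so d_high − d_low has variance V/[p(1 − p)]. If d_low = 0, interaction z = overall z × √[(1 − p)/p].

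- p = 0.6: 2.80 × 0.816 = 2.29, power about 63%.
- p = 0.3: 2.80 × 1.53 = 4.28, power about 99%.

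**4. Smallest detectable difference between the two effects.** Take 2.80 times the SE of the difference between two stratum risk differences, with binomial variances and no design effect. Over a range of assumed control rates this gives:

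- Scenario 1 (0.30/0.30 to 0.70/0.13): about 15 to 16 points.
- Scenario 2 (0.60/0.60 to 0.80/0.30): about 15 to 17 points.

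The Scenario 2 range is optimistic. The same method gives an overall MDE of 8.6 points there, well below the SAP's figure. If the SAP's stated MDE is taken as its 80%-power point, the interaction MDE is MDE/√[p(1 − p)]. That is 13.2/0.490 = 26.9 points, or 22.0 points if 10.8 is right. In Scenario 1 it is 7.2/0.458 = 15.7 points, in line with the direct calculation.

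**The case against.** The best defence is that the outcome choice is sound. The protocol's dilution argument compares the indicator with the continuous score, and the indicator does focus on the margin the protocol cares about. Research question 1 asks whether the programme reduces conduct problems, and one overall effect answers that. Who benefits most by conduct status is not itself a research question, and the protocol promises only insight. All of this stands, and it limits the point to the claim about who benefits.

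The defence can add that practitioner-rated risk is already a moderator, and that another underpowered subgroup settles little. Practitioner risk is a different construct from a different rater. Limited power is a reason to label the split exploratory, as the SAP does for its other subgroups. It does not justify leaving out the moderator the protocol itself singles out.

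Three stronger readings are tempting, and the documents do not support them.

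- A reader might infer that those below the cut-off at baseline cannot improve, so that dilution is built in. They can benefit by not entering the high range, so dilution follows only if the effect in them is zero or smaller.
- A reader might infer that the binary outcome is invalid. It is not.
- A reader might take power within the baseline-high group as reassurance. Under the Step 3 assumptions its z is 1/√0.6 = 1.29 times the overall z, for about 95% power. That tests whether the group benefits at all, not whether it benefits more than the others.

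**Conclusion.** The point holds for the inference about who benefits most. Followed as written, the plan cannot show whether young people high at baseline gain more than the rest, although the protocol gives that insight as a reason for its outcome. The primary estimate, its validity and the sample size are unaffected.

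If there is no effect below the cut-off and 60% start above it, a 13.2-point overall effect stands for 22 points in the baseline-high group (18 points if the SAP's 10.8 is right). The interaction then has about 63% power when the overall test has 80%, assuming equal variance and design effect. At a share of 0.3 the same premise gives about 99%, but the SAP regards the later baseline estimates behind 0.6 as more reliable. The detectable difference is about 15 to 17 points before any design effect, and larger in Scenario 2 on the SAP's own stated precision. The added split is worth pre-specifying, but only as exploratory.

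**What to change.** 1. Add treatment by baseline high/very-high conduct status to research question 4, Protocol Step 8 and SAP Subgroup analyses, as a pre-specified exploratory analysis, so that the three lists agree on this moderator.
2. Report the effect on the primary outcome with its 95% CI in the baseline-high group (recovery) and the baseline-not-high group (new onset), together with the interaction test. Use the primary model's fixed effects and clustering.
3. State how young people with a missing baseline conduct score are handled in this split, in line with the SAP's Missing data section.
4. Reword research question 1 and the Primary outcome section so that insight into who benefits most refers to this analysis. The endline indicator can still be defended there as targeting the relevant margin.
5. Reconcile 22% of 0.60 (13.2 points) with the printed 10.8 points in the SAP's discussion of MDEs.

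The cost is one interaction term on data already planned for collection. The downside is one more exploratory test with limited power, so a non-significant interaction should not be read as evidence that the two groups respond alike.
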